2.1.1.5 ECOG performance status  $\leq 2$

2.1.1.6 Serum creatinine within 3 weeks prior to Eovist MRI  $\leq 1.8$ mg/dl and estimated glomerular filtration rate (eGFR) must be  $>30$  ml/min/1.73m^2.

2.1.1.7 Patients must have normal liver function as defined below:

- total bilirubin  $< 2X$  normal institutional limits or  $>3.0$  mg/dl in patients with Gilbert's syndrome
- AST(SGOT) and ALT(SGPT)  $\leq 3$  X institutional upper limit of normal

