2.1.1.8 Ability of subject to sign a written informed consent document

#### 2.1.2 Exclusion Criteria

2.1.2.1 Subjects with known hypersensitivity and allergy to gadolinium contrast agents

- 2.1.2.2 Subjects with any coexisting medical or psychiatric condition that is likely to interfere with study procedures and/or results
- 2.1.2.3 Subjects with severe claustrophobia unresponsive to oral anxiolytics
- 2.1.2.4 Subjects with contraindications to MRI
- 2.1.2.5 Subjects weighing >136 kg (weight limit for scanner table)
- 2.1.2.6 Subjects with pacemakers, cerebral aneurysm clips, shrapnel injury, or other implanted electronic devices or metal not compatible with MRI
- 2.1.2.7 Subjects with other medical conditions deemed by the principle investigator (or associates) to make the subject ineligible for protocol procedures
- 2.1.2.8 Subjects who will have a delay in clinically indicated radiation therapy due to the interval between Eovist® MRI imaging and biopsy

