## **2.3 Registration Procedures**

Authorized staff must register an eligible candidate with NCI Central Registration Office (CRO) within 24 hours of signing consent. A registration Eligibility Checklist from the web site (<http://home.ccr.cancer.gov/intra/eligibility/welcome.htm>) must be completed and faxed to [contact]. After confirmation of eligibility at Central Registration Office, CRO staff will call pharmacy to advise them of the acceptance of the patient on the protocol prior to the release of any investigational agents. Verification of Registration will be forwarded electronically via e-mail to the research team. A recorder is available during non-working hours.

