### **3.6.1 Study Periods**

#### **3.6.1.1 Screening Period**

A screening visit will be performed within 21 days before administration of Eovist®. Subjects will be permitted to continue taking any routine or necessary medication.

All subjects must satisfy all the eligibility criteria listed in Section [2.1](#). Signed and dated informed consent must be obtained from all subjects before any study-specific procedures are performed.

The following data will be collected:

- Date of birth
- Weight
- Height
- Prior and concurrent medications
- Medical history and concurrent diseases
- Results of screening tests: laboratory tests

Personal data (including contact information) will be collected with the subject's permission and only to the extent that is necessary for the purposes of the study. Blood samples for laboratory tests will be drawn. Vital signs (i.e., systolic and diastolic blood pressure, heart rate, body temperature, and respiration rate) will be recorded.

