**Table 1 Clinical Laboratory Variables**

Serum Biochemistry	Hematology
--------------------	------------

Alanine aminotransferase	Hematocrit
Albumin	Hemoglobin
Alkaline phosphatase	Platelet count
Aspartate aminotransferase	Red blood cell count
Bilirubin (total, direct)	White blood cell (WBC) count
Calcium	
Chloride	
Creatinine	
Glucose	
Potassium	
Sodium	
Urea nitrogen	
PSA	

Blood samples will be obtained for assessment of serum biochemistry and hematology parameters as described in the Study Calendar (Section 3.6). The maximum amount of blood taken for these tests will not be more than 60 ml.

Interpretation and follow-up of abnormal laboratory test results should be conducted in conjunction with the clinical situation of the subject and in consultation with the referring physician.

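### The bilirubin limit for men with Gilbert's syndrome in inclusion criterion 2.1.1.7 is written as a floor (>3.0 mg/dl) where a ceiling is needed

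*Combined protocol and SAP*

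**What the plan says.** Criterion 2.1.1.7 opens with "Patients must have normal liver function as defined below" and then gives two bullets.

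- **Total bilirubin:** below 2X normal institutional limits, or ">3.0$ mg/dl in patients with Gilbert's syndrome".
- **AST and ALT:** at most 3 "X institutional upper limit of normal".

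The criterion is binding. Section 3.6.1.1 states: "All subjects must satisfy all the eligibility criteria listed in Section" 2.1. Bilirubin is measured in every subject: the hepatic panel is a screening test (Section 2.2.1.1), and Table 1 lists "Bilirubin (total, direct)" among the serum biochemistry variables. Section 2.3 routes enrolment through an eligibility checklist and confirmation by the Central Registration Office.

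**The concern.** A criterion meant to secure normal liver function should cap bilirubin. For men with Gilbert's syndrome it sets a minimum instead. A clause of this kind would normally allow these men a somewhat higher ceiling. As printed, it accepts higher values without limit and refuses some or all of the lower ones, depending on how the word joining the two limits is read.

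This is an operative eligibility threshold. Staff who follow the text could enrol a man with marked hyperbilirubinaemia and turn away one with a mild elevation. Staff who follow the evident intent depart from the approved protocol. Section 9.1.8 counts any such departure as a deviation, and Section 9.2.1 requires all deviations to reach the IRB within 7 working days.

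**Working it through.** No power or sample-size figure is involved. The check is to compare the direction of the limits, work out which values the rule admits, and look for a repair elsewhere.

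**1. Direction of each limit in 2.1.1.7**

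| Limit | As written | Type |
|---|---|---|
| Total bilirubin, general | < 2X institutional limit | ceiling |
| Total bilirubin, Gilbert's syndrome | > 3.0 mg/dl | floor |
| AST and ALT | ≤ 3X upper limit of normal | ceiling |

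**2. Values admitted for a man with Gilbert's syndrome**

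Let x be his total bilirubin in mg/dl and U the institutional limit.

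- *Reading A, the clause is an alternative:* he meets the bilirubin limit if x < 2U or x > 3.0. He is refused if 2U ≤ x ≤ 3.0, a band of width 3.0 − 2U.
- *Reading B, the clause replaces the general limit:* he meets it only if x > 3.0. Every value at or below 3.0 is refused, including a normal one.

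The documents do not give U. Under Reading A, with assumed values:

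| Assumed U (mg/dl) | 2U | Refused band | Width |
|---|---|---|---|
| 1.0 | 2.0 | 2.0 to 3.0 | 3.0 − 2.0 = 1.0 |
| 1.2 | 2.4 | 2.4 to 3.0 | 3.0 − 2.4 = 0.6 |
| 1.5 | 3.0 | 3.0 only | 3.0 − 3.0 = 0 |

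The missing ceiling needs no assumption about U: a value of 10 mg/dl meets the bilirubin limit under both readings, since 10 > 3.0. By contrast, under Reading A a man at 2.5 mg/dl is refused if U is 1.0 or 1.2.

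**3. Search for a repair elsewhere**

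- The eligibility list in the Precis does not mention liver function.
- The exclusion criteria in 2.1.2 contain no hepatic limit.
- Section 2.2.1.1 and Table 1 provide for the measurement but set no threshold.
- The AST/ALT limit does not bound bilirubin.
- Exclusion 2.1.2.2 ("Subjects with any coexisting medical or psychiatric condition that is likely to interfere with study procedures and/or results") and exclusion 2.1.2.7 ("Subjects with other medical conditions deemed by the principle investigator (or associates) to make the subject ineligible for protocol procedures") are discretionary. They can remove an unsuitable man. They set no ceiling and cannot admit a man whom the inclusion criterion refuses.

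**4. Rule with the sign reversed**

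With x < 2U or x ≤ 3.0, and U between 1.0 and 1.5, these men qualify at every value up to 3.0 mg/dl and at none above it. The gap closes and the ceiling is restored.

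**The case against.** The strongest reply is that this is an obvious one-symbol slip. The criterion's opening words and the neighbouring limits show what was meant, few men are affected, and no analysis depends on it. Central confirmation of eligibility (Section 2.3) and the investigators' re-evaluation after each patient (Section 9.3.1) make an unnoticed literal application less likely. The human toxicity section (10.2.2) names renal and hypersensitivity risks, not a bilirubin-related one, so the documents show no specific harm. Reading B is arguably the less natural reading, because the two limits are joined by an alternative. The refused band under Reading A could shrink to a single value. Finally, the text was read from PDF by a program, so a misread symbol is conceivable.

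Much of this stands as a limit on the size of the problem. The number affected is small, the width of the band is unknown, and no harm to a subject is demonstrated. It does not remove the error. The missing ceiling follows under either reading and without any assumed institutional limit. An intent that is easy to infer is a reason to correct the text, because acting on it uncorrected creates a reportable deviation, and a checklist copied from the protocol would carry the same sign. A misread is unlikely: 2.1.1.6 and 2.1.1.7 print <, ≤ and > as distinct symbols, and the eGFR requirement of >30 in 2.1.1.6 is correctly a lower bound. The sponsor can settle this from the source page.

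**Conclusion.** The concern holds: the Gilbert's clause is wrong as written. Under both readings, men with Gilbert's syndrome have no bilirubin ceiling. Reading A also refuses a band of width 1.0, 0.6 or 0 mg/dl at assumed institutional limits of 1.0, 1.2 or 1.5 mg/dl; Reading B refuses every value at or below 3.0 mg/dl. The documents do not say how many men with Gilbert's syndrome to expect, and few of the 25 planned in Section 7.1 are likely to be affected. Power, sample size and the primary analysis are unchanged. The correction should be made because the threshold is binding, not because the trial's results are at risk.

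**What to change.** Turn the clause into an upper limit, for example: total bilirubin <2X the institutional upper limit of normal, or ≤3.0 mg/dl in patients with Gilbert's syndrome. The sponsor should confirm the value and whether the bound is strict, since the documents settle neither. Naming the upper limit of normal in the general clause also brings it into line with the AST/ALT bullet.

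Then check the form named in Section 2.3 ("A registration Eligibility Checklist from the web site"), whose wording is not in the documents, to see that it gives the limit in the same direction.

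The cost is a small wording correction to the protocol and a check of one form. Sample size, procedures and analysis stay as they are.

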2.1.1.8 Ability of subject to sign a written informed consent document

#### 2.1.2 Exclusion Criteria

2.1.2.1 Subjects with known hypersensitivity and allergy to gadolinium contrast agents

- 2.1.2.2 Subjects with any coexisting medical or psychiatric condition that is likely to interfere with study procedures and/or results
- 2.1.2.3 Subjects with severe claustrophobia unresponsive to oral anxiolytics
- 2.1.2.4 Subjects with contraindications to MRI
- 2.1.2.5 Subjects weighing >136 kg (weight limit for scanner table)
- 2.1.2.6 Subjects with pacemakers, cerebral aneurysm clips, shrapnel injury, or other implanted electronic devices or metal not compatible with MRI
- 2.1.2.7 Subjects with other medical conditions deemed by the principle investigator (or associates) to make the subject ineligible for protocol procedures
- 2.1.2.8 Subjects who will have a delay in clinically indicated radiation therapy due to the interval between Eovist® MRI imaging and biopsy

## **2.2 Screening Evaluation**

Subjects will be seen in either the UOB, ROB or MOB clinics by members of [name], [name] and/or [name] teams, respectively. Conventional imaging studies confirming presence of metastatic soft tissue or metastatic bone prostate cancer lesions (outside imaging studies are acceptable for study entry) will be reviewed by the Molecular Imaging Program staff.

### **2.2.1 Screening tests:**

Screening Test must be completed within 21 days prior to the injection of Eovist®

#### **2.2.1.1 Evaluations:**

- vital signs (BP, HR, RR, & Temperature)
- clinical laboratory assessments (CBC w/diff, Acute Care Panel, Hepatic Panel, Mineral Panel, & PSA)
- OATP1B3 genotype analysis of blood samples will be done in [name] lab; results will not be a part of the study eligibility criteria.

## **2.3 Registration Procedures**

Authorized staff must register an eligible candidate with NCI Central Registration Office (CRO) within 24 hours of signing consent. A registration Eligibility Checklist from the web site (<http://home.ccr.cancer.gov/intra/eligibility/welcome.htm>) must be completed and faxed to [contact]. After confirmation of eligibility at Central Registration Office, CRO staff will call pharmacy to advise them of the acceptance of the patient on the protocol prior to the release of any investigational agents. Verification of Registration will be forwarded electronically via e-mail to the research team. A recorder is available during non-working hours.

### 3 STUDY IMPLEMENTATION

#### 3.1 Study Design

This is an open-label, single-center pilot study. Twenty evaluable subjects will be enrolled, 10 subjects with localized prostate cancer and 10 subjects with advanced prostate cancer with soft tissue or bone involvement. A subject is considered evaluable if he completes pre and post Eovist® injection MRI scans and has sufficient tissue for OATP1B3 IHC.

- Localized disease:
  - If existing pathologic tissue can be linked with confidence to an MRI-defined lesion (i.e. pathologic specimen is labeled as to location) then that tissue can be used for OATP1B3 expression.
  - Otherwise the tissue obtained during image guided biopsy at NCI will be used for OATP1B3 expression testing.
  - Prostatectomy specimens may be a source of tissue if the above sources are not available and the patient undergoes prostatectomy.
- Advanced disease:
  - If clinically acquired tissue is not available, the patient must be willing to have a percutaneous needle biopsy of a soft tissue lesion or metastatic bone lesion (measuring  $\geq 1.5\text{cm}$  in diameter at CT or MRI scan).

All tissue samples (either biopsy specimens from localized intraprostatic lesions or prostatectomy specimens in the localized disease arm or biopsy specimens from the soft tissue or metastatic bone lesions in the advanced disease arm) for immunohistochemical (IHC) analysis must be acquired within  $\pm 20$  weeks (assuming no intervening therapy) of Eovist® imaging.

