### **Design:**

- This pilot study will accrue 25 subjects divided into two arms: 10 evaluable subjects with localized prostate cancer and 15 evaluable subjects with advanced disease
- Each subject will receive a single IV dose of Eovist® by bolus injection
- All subjects will undergo MRI prior to and immediately after, 10, 20 and 60 minutes post-Eovist® injection

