### **3.1.3 Pathology**

#### **3.1.3.1 Surgical Pathology**

[figure not shown]
[figure not shown]
For the localized disease arm, biopsy specimens obtained from intraprostatic lesions or prostatectomy specimens will undergo standard preparation and sectioning in the Laboratory of Pathology for pathological diagnosis. The biopsy procedures for the localized disease arm will be part of standard of care.

For the advanced disease arm, biopsy specimens obtained from distant lesions will undergo standard preparation and sectioning in the Laboratory of Pathology for pathological diagnosis. The biopsy procedure for the advanced disease arm will be research biopsies and will be performed under imaging (ultrasound or CT) guidance.

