### **3.9 Off-Study Criteria**

Patients will be taken off study once all study procedures are complete. In cases where a subject withdraws or is withdrawn from the study after administration of Eovist® and before biopsy is performed, a replacement subject will be enrolled.

Should a subject withdraw after administration of Eovist®, or should the investigators decide to withdraw the subject, all efforts will be made to complete and report the protocol-stipulated observations up to the time of withdrawal as thoroughly as possible. A final evaluation at the time of the subject's withdrawal should be made and an explanation given of why the subject is withdrawing or being withdrawn from the study. The reason and date and time of withdrawal must be recorded. If the reason for withdrawal is a clinical AE, monitoring will continue until the outcome is established.

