## **7 STATISTICAL CONSIDERATIONS**

### **7.1 Study Populations**

25 evaluable patients will be included in this trial with an accrual rate of 1-2 patients a month. Therefore, it is expected that this study enrollment will be completed within 1.5 years and full study goals within 2.5 years. We plan to enroll 25 evaluable patients (10 in arm 1 and 15 in arm 2).

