#### **7.4 Sample Size Determination**

Sample size and power calculation is based on comparing signal change between pre- and post-injection in each subgroup separately. Based on a prior study on liver cancer patients, up to 3-fold mean signal change may be detected and the standard deviation of log-transformed signal ratio is approximately 0.25. With 10 evaluable patients in subgroup 2 (late stage), there is more than 95% power to detect a 2-fold mean signal change between pre- and post-injection at 5% significance level. For the first subgroup, OATP1B3 expression is likely lower and hence smaller signal change is expected. With 10 evaluable patients in each of these two subgroups, there is 83% power to detect a minimal 1.2 fold mean signal change. Higher power may be achieved if each patient has multiple lesions. Signal changes of multiple lesions from the sample patients will be averaged, and the comparison is based on the paired t-test using log-transformed signal values on a subject basis.

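### The advanced-disease arm has two evaluable targets, 10 in section 3.1 and 15 in the precis and section 7.1, and section 7.4 gives power only at 10

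*Combined protocol and SAP*

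**What the plan says.** Four places bear on the number of subjects.

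- Section 3.1 (Study Design): "Twenty evaluable subjects will be enrolled, 10 subjects with localized prostate cancer and 10 subjects with advanced prostate cancer". It defines a subject as evaluable if he completes the MRI scans before and after injection and has enough tissue for OATP1B3 immunohistochemistry.
- Precis (Design): a total of 25, made up of "10 evaluable subjects with localized prostate cancer and 15 evaluable subjects with advanced disease".
- Section 7.1 (Study Populations): "We plan to enroll 25 evaluable patients (10 in arm 1 and 15 in arm 2"), with accrual of 1-2 patients a month and enrolment complete within 1.5 years.
- Section 7.4 (Sample Size Determination): power is worked out in each subgroup separately, by a paired t-test on log values at the 5% level, taking it that "the standard deviation of log-transformed signal ratio is approximately 0.25". It then states: "With 10 evaluable patients in subgroup 2 (late stage), there is more than 95% power to detect a 2-fold mean signal change", and "With 10 evaluable patients in each of these two subgroups, there is 83% power to detect a minimal 1.2 fold mean signal change". The number 15 does not appear there.

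Section 3.9 adds that if a subject withdraws or is withdrawn after injection and "before biopsy is performed, a replacement subject will be enrolled". On tissue, section 3.1.3.1 says: "The biopsy procedure for the advanced disease arm will be research biopsies". Section 3.1 requires willingness to have a percutaneous biopsy when clinically acquired tissue is not available.

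**The concern.** The evaluable target tells staff when an arm is complete. After the tenth evaluable advanced subject, the arm is full under section 3.1 and five short under the precis and section 7.1. Whichever is followed, another section of the protocol is not. Section 9.1.8 counts any departure from the approved protocol as a deviation, and section 9.2.1 requires all deviations to be reported.

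The five subjects would receive the contrast agent, and those without available tissue would have a biopsy done for research. Section 8.1 describes the study as more than minimal risk with no direct benefit expected, so the number exposed should be single and justified.

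The power statement in 7.4 fits the 10+10 design. For the 10+15 design in 7.1 it describes the localized arm but not the advanced arm, so the size of that arm has no stated statistical basis.

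**Working it through.** **1. The counts side by side**

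| Place | Localized | Advanced | Total |
|---|---|---|---|
| Precis | 10 | 15 | 25 |
| Section 3.1 | 10 | 10 | 20 |
| Section 7.1 | 10 | 15 | 25 |
| Section 7.4 (power) | 10 | 10 | not stated |

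The difference is 25 − 20 = 5, all in the advanced arm.

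**2. Can the documents reconcile them?**

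- Enrolled versus evaluable: no. The arm figures in the precis, 3.1 and 7.1 are all evaluable counts.
- Dropout allowance: no, for the same reason. Section 3.9 also replaces subjects lost between injection and biopsy.
- Accrual: no. 18 months × 1-2 a month = 18-36 patients, which contains both 20 and 25.
- Weight of text: no. The precis and 7.1 support 15, while 3.1 and 7.4 support 10.

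**3. Reproducing the stated 83% at n = 10**

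Inputs from 7.4: SD 0.25, 1.2-fold change, 5% level, paired t-test. Neither the log base nor the sidedness is given; two-sided is assumed first. Power comes from the noncentral t distribution with n − 1 degrees of freedom and noncentrality log(fold) / SD × √n.

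- Log2: log2(1.2) = 0.263; noncentrality 0.263 / 0.25 × √10 = 3.33; power 84.1%, close to the stated 83%.
- Natural log: ln(1.2) = 0.182; noncentrality 0.182 / 0.25 × √10 = 2.31; power 53.9%. Reaching 83% would need n = 18.
- Natural log with SD 0.25/√2 = 0.177: power 82.6%. Log2 is therefore not the only reading near 83%, and the base remains an assumption.
- One-sided at n = 10: 92.2% on log2 and 68.6% on natural log, so neither matches.

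For a 2-fold change at n = 10, two-sided, power is above 99.9% on log2 and natural log. This agrees with the stated figure of more than 95%.

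**4. The figures missing from 7.4, at n = 15 (two-sided 5%)**

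| Assumed scale of the SD | Power for 1.2-fold, n = 10 | n = 15 | Fold change with 83% power, n = 10 | n = 15 |
|---|---|---|---|---|
| Log2, SD 0.25 | 84.1% | 96.6% | 1.20 | 1.15 |
| Natural log, SD 0.25 | 53.9% | 74.8% | 1.30 | 1.22 |
| Natural log, SD 0.25/√2 | 82.6% | 96.0% | – | – |

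For a 2-fold change, power at n = 15 is also above 99.9% on log2 and natural log with SD 0.25.

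**5. Illustration only: the correlation in subgroup 2 (section 7.3.2)**

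The plan promises no power for this analysis. The smallest correlation significant at two-sided 5% is t / √(n − 2 + t²). At n = 10, t = 2.306 and |r| = 0.63. At n = 15, t = 2.160 and |r| = 0.51. For an assumed true r of 0.6, simulated Pearson power is about 49% at 10 and 70% at 15. The simulation assumes bivariate normal data, so it is approximate for the 0-3 staining grade in section 3.5.3.

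**The case against.** The strongest reply is that nothing analytical breaks. The primary test is the same at 10 or 15, and power at 15 is higher. The n of 10 in 7.4 is right for the localized arm under either design. For the advanced arm it gives a lower bound, so the claim of more than 95% power for a 2-fold change survives. The precis and 7.1 agree on 25 with an explicit split, which suggests that 3.1 was simply not updated. Section 3.1 also states a number to enrol, not a formal closing rule.

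The point about power stands: choosing 15 loses none. The suggestion that 3.1 is out of date is plausible but cannot be shown, because 7.4 shares its figure of 10. If 3.1 is out of date, so is 7.4. No formal closing rule is written, but the number to enrol is the only stopping point the plan gives the arm when recruitment runs its normal course, and there are two such numbers.

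Two limits are fair. Some front matter is missing from the public copy and the Figure 1 schema is not shown, so a reason for 15 may exist there; it is absent from the text available. Replacement under section 3.9 covers only withdrawal between injection and biopsy, not every route to being non-evaluable. The conclusion that the gap is not a dropout allowance therefore rests on both targets being evaluable counts, with 3.9 as support.

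**Conclusion.** The concern holds and must be fixed. The current text sets the advanced arm at both 10 and 15 evaluable subjects and the trial at both 20 and 25. The power statement matches only the smaller design. This part rests on reading the sections against each other and needs no statistical assumption.

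The defect is a target that cannot be followed as written and a power statement that does not cover the larger design. It is not a loss of power. The power gained by going from 10 to 15 depends on the unstated log base: about 12 percentage points for a 1.2-fold change on log2 (96.6 − 84.1 = 12.5) and about 21 on natural log (74.8 − 53.9 = 20.9), both with SD 0.25 and a two-sided 5% test.

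**What to change.** The sponsor should confirm one target and make the precis, 3.1, 7.1 and 7.4 agree. The target can be corrected at once. Before any power is restated, 7.4 should name the log base of the SD of 0.25 and say whether the 5% level is one- or two-sided.

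- **If 10+15 is intended:** change 3.1 to twenty-five evaluable subjects, ten localized and fifteen advanced. Recompute 7.4 by arm, with subgroup 1 at n = 10 and subgroup 2 at n = 15. Give the reason for 15.
- **If 10+10 is intended:** change the precis and 7.1 to 20 (10 and 10). The n in 7.4 then matches; recheck its 83% once the base is stated.

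The cost is text edits and one recalculation. Relative to 3.1, keeping 25 means five more advanced subjects, already counted in 7.1, and those without available tissue would need a research biopsy. Choosing 20 needs no extra subjects.
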